### 8.1.3 Power and Sample Size

Based upon RTOG 9501, we expect that DFS at 1 year and 3 years will be 65.4% and 53.5% respectively for patients with high risk features undergoing CRT. We expect to reach similar DFS in this study. We expect that at least 50% of patients (~40 patients) based on defined inclusion criteria will have high risk disease confirmed at resection (+ECE or + margins). With an expected sample size of at least N=40 in the CRT arm, and adding Pembrolizumab to Cisplatin and radiation, we expect to reach over 80% power to detect an increase of 21% in DFS at year 1 (86% DFS compared to 65% at 1 year) using the one-sample exact test at significance level, alpha=0.025 (one-sided). In comparison, assuming that we will reach a similar 1 year DFS of 68.8% in the radiation alone arm, by adding Pembrolizumab, and assuming N=40, we expect to reach over 80% power to detect an increase of 19% in DFS at 1 year (88% DFS compared to 69% at 1 year). Every effort will be made to ensure that we have 40 patients either reached the DFS endpoints or were followed for at least one year without disease recurrence in both strata.

### 8.1.4 Accrual Rate

At the University of Cincinnati, we see approximately 150 new cases of surgically treatable (oral cavity, larynx, hypopharynx) stage III/IV HNSCC per year. Of those, approximately 100% oral cavity, > 50% larynx, and 50% hypopharynx receive surgical resection and about 40%

require adjuvant therapy. We therefore, expect to accrue approximately 1-2 patients per month at UC. Per discussions with our other sites (OSU, Univ of Louisville, MUSC, USCD and Univ of Mich, MD Anderson) we expect to add ~ 1-2 patients a month from each as well. Therefore, we expect enrollment for this phase II study to be completed within 1 year based on 80 patients.

## 8.2 Statistical Analysis Plan

### 8.2.1 Safety Endpoints

The safety endpoints are all adverse events graded from 1 to 5 described in Section 7.

The Lead-in population will be assessed for DLTs as described in section 5.2.2.3.1.

### 8.2.2 Efficacy Endpoints

#### Primary Endpoint

Disease Free Survival (DFS): measured from the time of treatment allocation to the time of discovery of the first evidence after treatment of any tumor (local, regional, metastatic, or second primary) or death from any cause. DFS at 1 and 3 years will be the primary efficacy endpoints.

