#### 4.2.3.2 Efficacy Endpoints

This is a phase II non-randomized study and therefore will rely on historical controls for the primary efficacy endpoint of disease free survival (DFS) in resected high risk HNSCC. Based on the pivotal RTOG 9501 and EORTC 22931 adjuvant studies, disease free survival at 1 year was approximately 66% and 76% respectively for the CRT arms and 58% and 72% respectively for radiation only arms (See table). The 3 year estimates are somewhat closer between the two studies.

Study Group	RTOG 9501		EORTC 22931	
	RT	CRT	RT	CRT
Disease Free Survival 1 year	58%	66%	72%	76%
Disease Free Survival 3 year	37%	47%	40%	57%

There were several differences in these studies including number of lymph nodes involved (94% had  $\geq 2$

lymph nodes in RTOG versus only 57% in EORTC) and the number of patients with at least 1 high risk feature (ECE or positive margins) was also different (approximately 70% of the patients in the EORTC and 59% of RTOG

18MAR2021

study) which may account for these differences.

Based on phase I data, Pembrolizumab resulted in response rates up to 46% at least in those patients positive for PD-L1. Therefore, we expect that the addition of Pembrolizumab will significantly reduce the chance of relapse in this population and therefore, will result in improved DFS. Most locoregional relapses (the most common cause of death in this group) occur within the first year. Therefore, our primary and secondary endpoints respectively will be DFS at 1 and 3 years, which will reflect early and late relapse. Our historical baseline will be based off the RTOG 9501 data due to the fact that entry criteria included either ECE, positive margins or  $\geq 2$  lymph nodes all of which are considered to be either high risk or high-intermediate risk which is the group we are most interested in for this study and encompasses our inclusion criteria.

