#### **8.1.2 Efficacy Analysis**

All patients who received  $\geq 1$  dose of Pembrolizumab will serve as the primary analysis population in this study. The primary efficacy endpoint is to estimate the disease-free-survival (DFS) (i.e., time from treatment allocation to documented first relapse) at 1 year and 3 years. Key secondary efficacy endpoints include overall survival (OS) (i.e., time from treatment allocation to death due to any cause) at 1 year and 3 years. After resection, patients will be stratified based on adverse risk features. Kaplan-Meier method will be used to estimate survival rates for DFS and OS at 1 and 3 years. The survival rates will be compared with historical censored data (RTOG 9501: 66% in CRT and 58% in RT) using the log-rank test.

We will use estimates of the 95% CI for RTOG 9501 for DFS at 1 and 3 years (see below obtained from RTOG), in order to compare our results.

Study Group	RTOG 9501	
	RT Intermediate Risk	CRT High Risk
Disease Free Survival 1 year (95%CI)	68.8% (59.4%-78.2%)	65.4% (57.1%-73.6%)
Disease Free Survival 3 year (95%CI)	44.1% (34%-54.2%)	45.5% (36.9%-54.2%)

We would expect that adding Pembrolizumab would increase the DFS above these rates in RTOG 9501 and that our results would not fall outside of the lower bound of the CI above.

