### **8.2.4.2 Disease Free Survival**

Kaplan-Meier method will be used to estimate the disease free survival rates at 1, 3 and 5 years among patients treated with combined Pembrolizumab, radiation therapy and +/- Cisplatin. 95% CI of these rates will be provided. These survival rates at 1 year will be estimated and compared with historical data (RTOG 9501: 65.4% in CRT and 68.8% in RT) via the one-sample exact test, point and confidence interval estimation. We will also use the log-rank test and Cox model to compare the DFS between the trial data and the historical data if patient level data obtained from RTOG 9501. An interim analysis will be done throughout study at the PI and statistician discretion.

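### The plan does not fix which time point or which comparison decides the primary DFS question in each stratum

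*Combined protocol and SAP*

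**What the plan says.** **Which time point is primary.** Section 8.2.2: "DFS at 1 and 3 years will be the primary efficacy endpoints". Section 8.1.2 and primary objectives 2 and 3 in section 3.1 also name both 1 and 3 years. Section 4.2.3.2 differs: "our primary and secondary endpoints respectively will be DFS at 1 and 3 years".

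**Which comparison is made.**
- Section 8.1.2: "The survival rates will be compared with historical censored data (RTOG 9501: 66% in CRT and 58% in RT) using the log-rank test". No condition is attached. The section also prints RTOG 9501 rates with 95% CIs at 1 and 3 years and says that results will be read against them.
- Section 8.1.3 gives the sample size ("With an expected sample size of at least N=40 in the CRT arm", and 40 assumed in the RT stratum) and a power of over 80% at 1 year, "using the one-sample exact test at significance level, alpha=0.025 (one-sided".
- Section 8.2.4.2 compares the 1-year rates with 65.4% (CRT) and 68.8% (RT) "via the one-sample exact test, point and confidence interval estimation". It continues: "We will also use the log-rank test and Cox model to compare the DFS between the trial data and the historical data", on condition that patient-level RTOG 9501 data are obtained. For 3 years it gives a Kaplan-Meier estimate with a 95% CI and names no test.

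No section says which of these decides, sets an order among the methods, divides alpha or calls any of them supportive.

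**The concern.** Each stratum has one directional hypothesis in section 3.1, that adding pembrolizumab increases DFS over historical data. Several comparisons could be read as answering it. They ask different questions: a rate at 1 year, a rate at 3 years, and the whole curve. Without a named deciding analysis, two readers following different sections could draw opposite conclusions from the same data. The one-sided 0.025 in 8.1.3 would then protect only one of the ways in which success might be claimed.

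**Working it through.** **1. The plan's own figure.** Inputs: n=40 per stratum and one-sided 0.025 (8.1.3); nulls 65.4% and 68.8% (8.2.4.2); alternatives 86% and 88% (8.1.3). The critical count is the smallest r with P(X ≥ r | n=40, p0) ≤ 0.025.
- CRT: P(X ≥ 32 | 0.654) = 0.034 and P(X ≥ 33 | 0.654) = 0.0141, so r = 33. Power P(X ≥ 33 | 0.86) = 0.811.
- RT: P(X ≥ 33 | 0.688) = 0.040 and P(X ≥ 34 | 0.688) = 0.0163, so r = 34. Power P(X ≥ 34 | 0.88) = 0.802.

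The stated power of over 80% reproduces. The actual size of the test is 1.4% (CRT) and 1.6% (RT); 2.5% is a ceiling.

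**2. Two time points, each tested at exactly 0.025 (assumption).** The correlation between the 1- and 3-year proportions in the same patients is ρ = √[S3/(1−S3) × (1−S1)/S1]. The chance that at least one succeeds is 1 − Φ₂(1.96, 1.96; ρ).
- CRT, 3-year null 45.5% (table in 8.1.2): ρ = √(0.455/0.545 × 0.346/0.654) = 0.66, giving 4.3%.
- CRT, 3-year null 53.5% (text of 8.1.3): ρ = 0.78, giving 4.0%.
- RT, 3-year null 44.1%: ρ = √(0.441/0.559 × 0.312/0.688) = 0.60, giving 4.4%.

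**3. Any route, simulated under the null.** Assumptions: piecewise-exponential DFS through the 1- and 3-year null rates, exact tests at both time points, a two-sample log-rank test at z < −1.96, follow-up of 3 or 5 years, and no dropout. The printed 1-year CIs imply historical samples of p(1−p)/SE². For CRT, SE = (0.736−0.571)/3.92 = 0.0421, so n is about 128. For RT, SE = (0.782−0.594)/3.92 = 0.0480, so n is about 93. Historical samples of 95 to 200 were tried.

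| Stratum and 3-year null | 1-year exact alone | 1- or 3-year exact | Either, or log-rank |
|---|---|---|---|
| CRT, 45.5% | 1.4% | 3.1% | 3.7-4.4% |
| CRT, 53.5% | 1.4% | 2.0% | about 3.2-3.6% |
| RT, 44.1% | 1.6% | 2.8% | 3.6-4.1% |

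The 53.5% row used a historical sample of about 127. Repeat runs of 8,000 to 20,000 trials with historical samples of 127 and 93 gave 3.6-4.5% (CRT, 45.5%) and 4.0-4.9% (RT). A one-sample log-rank gave 2.4-4.5%. If all three tests had size exactly 2.5%, the rate would be 4.1-5.8%. Independence would give 1 − 0.975³ = 7.3%, but these statistics are positively correlated. The overall range is about 2-6%.

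**4. Disagreement between routes (CRT, 5-year follow-up, year 1-3 hazard carried forward).**
- Early-only gain (80% at 1 year, 45.5% at 3 years): the exact test succeeds in about 44% of trials, the log-rank in 1%.
- Late-only gain (65.4%, then 60%): 1-2% against about 55%.
- Proportional hazards with a true 1-year DFS of 78%: the two disagree in 36-38% of trials.

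The size of the gap depends on follow-up. A check with follow-up cut at 3 years (6,000 trials, other settings unchanged) gave 44% against 4% for the early-only gain and 2% against 24% for the late-only gain.

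**5. The 1-year confidence interval.** At 32/40 (80.0%) in CRT the exact one-sided p is 0.034, which fails. The 95% lower limits, against 65.4%, are:
- plain Greenwood: 0.80 − 1.96√(0.8×0.2/40) = 67.6%, above the null
- log-log: 64.0%, below the null
- Clopper-Pearson: 64.4%, below the null

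Only the plain Greenwood limit conflicts with the exact test.

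**The case against.** The strongest reply is that the deciding test can already be inferred. The 1-year exact test is the only comparison with an alpha and a power, and 8.2.4.2 assigns it to the 1-year rates. Section 4.2.3.2 ranks 3-year DFS second. In the detailed methods, log-rank and Cox are additional analyses that may never be run. Objectives 2 and 3 and section 8.1.2 are phrased as estimation, and this is a non-randomized phase II trial with historical controls.

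Much of this stands. A reader might infer that every listed comparison is a formal test at 0.025, and so that the plan has a definite error rate such as 4.5% in place of 2.5%. The documents do not support that. They attach 0.025 to the 1-year exact test only and specify no 3-year test. Any figure needs an assumed curve shape, follow-up, form of log-rank, historical sample size and 3-year null. A reader might also infer that the plan never ranks the time points (4.2.3.2 does), or that its interval contradicts its test (the method is unnamed, and two of three common choices agree).

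The reply does not settle the point. Treating the exact test as decisive means inferring a decision rule from a power paragraph, against two primary time points in 8.2.2 and an unconditional log-rank in 8.1.2. The hypotheses in 3.1 are directional, so a claim is intended.

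**Conclusion.** The point holds as a contradiction and a missing decision rule. Sections 3.1, 8.1.2 and 8.2.2 conflict with 4.2.3.2 on the status of 3-year DFS. Sections 8.1.2, 8.1.3 and 8.2.4.2 differ on the comparison, and none says which result decides.

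On the assumption that any route could count at a nominal one-sided 0.025, the per-stratum false-positive rate is roughly 3-5%. The 2% end of the wider range comes from two exact tests with the 53.5% null, and the 6% end from three tests each of size exactly 2.5%. Disagreement between routes is the firmer reason to act, because it concerns what a result would mean as well as how often a false claim arises. The design and its stated power are sound, so this should be corrected but does not invalidate the trial.

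**What to change.** In 8.2.2 and 8.2.4.2, state that:
- the deciding analysis in each stratum is 1-year DFS by the one-sample exact test at one-sided 0.025, with each stratum its own claim. At N=40 and nulls of 65.4% and 68.8%, success needs at least 33/40 in CRT and 34/40 in RT; the count is recomputed if the stratum size differs;
- 3-year DFS, log-rank and Cox are supportive, are reported as estimates with 95% CIs, and cannot establish success alone.

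Align 3.1 (objectives 2 and 3), 4.2.3.2, 8.1.2 and the endpoint sentence in 8.2.2 with this. Make the log-rank in 8.1.2 conditional on patient-level data, as in 8.2.4.2. Report the 1-year CI by a method that agrees with the exact test (Clopper-Pearson when 1-year status is complete). In the same amendment, reconcile the historical rates: 66% and 58% in the text of 8.1.2 against 65.4% and 68.8% elsewhere, and 45.5% against 53.5% for 3-year CRT.

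Cost: a protocol and SAP amendment, because a primary endpoint and two primary objectives change status. No patients or data are added, and power stays at 81.1% and 80.2%. A positive 3-year or log-rank result alone could no longer be claimed as meeting the primary objective. Keeping both time points primary with 0.0125 each would raise the 1-year thresholds to 34/40 and 35/40 and cut the power of the 1-year test to about 68% and 65%.

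The discretionary interim analyses in 8.2.4.2 are a separate threat to alpha that this change does not address.

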#### Secondary Endpoints

Overall Survival (OS): defined as the time from randomization to death due to any cause. Subjects without documented death at the time of the final analysis will be censored at the date of the last follow-up. OS at 1 and 3 years will be used as secondary endpoints.

Locoregional Control: failure was defined as the reappearance of tumor in the original tumor bed or the development of cervical-node metastases after treatment.

Biomarker analysis including proportion of T cell population subsets before and after immunotherapy both in tumor tissue and peripheral blood.

#### Exploratory Endpoints

Change in serum cytokines and T cell functionality before and after immunotherapy. DFS and OS will also be measured at 5 years similar to above.

### 8.2.3 Analysis Population

### **8.2.3.1 Safety Analysis Population**

The All Patients as Treated (APaT) population will be used for the analysis of safety data in this study. The APaT population consists of all subjects who received at least 1 dose of study treatment. Only those patients who continue treatment after resection will be compared to RTOG 9501 historical controls. Those who receive only pre-resection Pembrolizumab will still be analyzed for safety but there will be no direct comparison. Subjects will be included in the treatment group corresponding to the trial treatment they actually received for the analysis of safety data. Subjects who take incorrect trial treatment for the entire treatment period will be included in the treatment group corresponding to the trial treatment actually received. At least one laboratory or vital sign measurement obtained subsequent to at least one dose of trial treatment is required for inclusion in the analysis of each specific parameter. To assess change from baseline, a baseline measurement is also required.

### **8.2.3.2 Efficacy Analysis Population**

The analysis of primary efficacy endpoints are based on all patients who received  $\geq 1$  dose of Pembrolizumab. Subjects will be included in the treatment group to which they are stratified after resection.

## **8.2.4 Statistical Methods**

### **8.2.4.1 Safety Analysis**

Descriptive statistics will be provided for safety endpoints. Exact test will be used to compare patients treated by Pembrolizumab + radiotherapy in this study with historical patients treated by radiotherapy only (targeted rate of grade 3 and 4 adverse effects is 39%) and compare patients treated by Pembrolizumab + radiotherapy + Cisplatin in this study with historical patients treated by radiotherapy + Cisplatin (targeted rate of grade 3 and 4 adverse effects is 50%).

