#### **4.2.2.2 Cisplatin**

Cisplatin is often given as either bolus dosing or weekly dosing when combined with radiation treatment in HNSCC. In locally advanced disease without surgical resection, patients are often offered bolus Cisplatin dosing at 100mg/m^2 days 1, 22 and 43 of radiation based off a pivotal study by Adelstein et al. The same dosing was used in the older adjuvant studies mentioned above but with a significant increase in toxicity over radiation alone especially in regards to increase in renal dysfunction, myelosuppression, ototoxicity and emetogenesis. In the post-operative setting, in which many patients have poor nutrition and decreased functional status, there is a concern that patients would not be able to tolerate this bolus dosing and other dosing schedules would be more ideal. Based on data from Ang et al. 2004, it was proposed that patients require at least a cumulative dose of 200mg/m^2 of Cisplatin regardless of the dosing schedule (fractionated, high dose, weekly). Weekly Cisplatin was also shown to be effective with concurrent radiation in nasopharyngeal cancer and was demonstrated to result in lower toxicity over the standard dosing, further strengthening a role for this dosing schedule in HNSCC. NRG has established weekly dosing to be the current standard for adjuvant studies and is currently being used in RTOG 1216 and 0920. Therefore, we feel weekly dosing (40mg/m^2 for 6 doses) is most appropriate in this patient population.

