#### Cisplatin

Cisplatin will be given at 40mg/m^2 starting concurrently with radiation one week after first post-surgery Pembrolizumab dose is given. Cisplatin will be given weekly for 6 doses during the radiation treatment. Any skipped doses will not be made up at the completion of radiation therapy.

**Formulation:** Each vial contains 10 mg of DDP, 19 mg of sodium chloride, 100 mg of mannitol, and hydrochloric acid for pH adjustment. One vial is reconstituted with 10 ml of sterile water. The pH range will be 3.5 to 4.5. Cisplatin injection also is available from the manufacturer in aqueous solution, each ml containing 1 mg Cisplatin and 9 mg NaCl and HCl or NaOH to adjust pH.

**Mechanism of Action:** The dominant mode of action of Cisplatin is inhibition of the incorporation of DNA precursors, although protein and RNA synthesis are also inhibited. Although Cisplatin is thought to act as an alkylating agent, there are data to indicate that its mode and sites of action are different from those of nitrogen mustard and other standard alkylating agents.

**Administration:** Cisplatin will be given as a bolus, infused over 1-2 hours along with appropriate hydration and anti-emetics.

**Storage and Stability:** Reconstituted solution of Cisplatin is stable for 20 hours when stored at 27°C and should be protected from light if not used within 6 hours. The vials and injection should not be refrigerated. Cisplatin has been shown to react with aluminum needles, producing a black precipitate within 30 minutes.

**Adverse Events:** Human toxicity includes nausea, vomiting, renal toxicity (with an elevation of BUN and creatinine and impairment of endogenous creatinine clearance, as well as renal tubular damage, which appears to be transient), ototoxicity (with hearing loss that initially is in the high-frequency range, as well as tinnitus), and hyperuricemia. Much more severe and prolonged toxicity has been observed in patients with abnormal or obstructed urinary excretory tracts. Myelosuppression, often with delayed erythrosuppression, is expected as well.

**Supply:** Cisplatin is commercially available. The use of drug(s) or combination of drugs in this protocol meet the criteria described under Title 21 CFR 312.2(b) for IND exemption.

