## **8.0 STATISTICAL ANALYSIS PLAN**

### **8.1 Statistical Analysis Plan Summary**

#### **8.1.1 Safety Analysis**

The All-Patients-as-Treated (APaT) population will be employed for safety analyses. The safety endpoints are all adverse events graded from 1 to 5. Fisher's exact test will be used to compare the proportion of adverse events among patients treated by Pembrolizumab + radiotherapy in this study with historical patients treated by radiotherapy only and compare patients treated by Pembrolizumab + radiotherapy + Cisplatin in this study with historical patients treated by radiotherapy + Cisplatin. Both the adverse events by grade as well as severe adverse event (SAE; yes/no) will be analyzed. RTOG 9501 data will be used for historical controls using targeted rates of 50% for CRT and 39% for RT. We expect that the addition of Pembrolizumab will not add undue toxicity over standard treatment and therefore, will give insight to the development of future trials.

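### The CRT safety comparison uses a 50% toxicity rate that the protocol traces to bolus cisplatin, and at 40 patients per arm a non-significant test could not show that no undue toxicity was added

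*Combined protocol and SAP*

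**What the plan says.** Section 8.1.1 names the comparator for both arms: "RTOG 9501 data will be used for historical controls using targeted rates of 50% for CRT and 39% for RT". Section 8.2.4.1 defines these as rates of grade 3 and 4 events and compares each arm with its rate by an exact test; for the cisplatin arm the "targeted rate of grade 3 and 4 adverse effects is 50" per cent. Section 8.1.1 calls the test Fisher's exact test and adds an expectation: "We expect that the addition of Pembrolizumab will not add undue toxicity over standard treatment".

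Section 4.2.2.2 describes the bolus schedule and says of the earlier trials: "The same dosing was used in the older adjuvant studies mentioned above but with a significant increase in toxicity over radiation alone". Sections 4.1.3 and 4.2.3.2 identify those trials as RTOG 9501 and EORTC 22931. For post-operative patients, section 4.2.2.2 says "there is a concern that patients would not be able to tolerate this bolus dosing". It then says that weekly cisplatin, in nasopharyngeal cancer, "was demonstrated to result in lower toxicity over the standard dosing, further strengthening a role for this dosing schedule in HNSCC". Section 5.2.3 fixes the schedule here: "Cisplatin will be given weekly for 6 doses during the radiation treatment".

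Sections 8.1 and 8.2 give no significance level, sidedness, acceptable excess, power or confidence interval for the safety comparison, and no rule for reading a non-significant result.

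**The concern.** The protocol argues for weekly cisplatin partly on tolerability, then compares weekly cisplatin plus pembrolizumab with a rate from the schedule it regards as harder to tolerate. If weekly dosing is milder in this population, the background rate without pembrolizumab lies below 50%. Some added toxicity would then have to accumulate before the arm even reached the benchmark. The plan does not mention or adjust for this.

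Separately, a test for a difference in about 40 patients has limited power for moderate excesses, even against a correct benchmark. This affects both arms. Side-effect frequency and severity form primary objective 1, and section 8.1.1 says the result should inform future trials. A result of no significant difference could carry more weight there than it can bear.

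**Working it through.** **Inputs from the documents.** Benchmarks are 50% (CRT) and 39% (RT), from 8.1.1 and 8.2.4.1. N=40 per arm comes from 8.1.3. Section 8.1.3 also gives an exact one-sample test at one-sided 0.025, but only for disease-free survival (DFS).

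**Assumptions.** The level for safety is not stated, so the DFS convention is borrowed and one-sided 0.05 is shown as well. The weekly-cisplatin background rate is not given, so a range of 30% to 45% is used.

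**Step 1: reproduce the plan's own power.** Reject if X ≥ r, where r is the smallest count with P(X ≥ r | n, p0) ≤ alpha. Power is P(X ≥ r | n, p1).

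- DFS, CRT: p0=0.654, n=40 gives r=33 and size 0.014. Power at 0.86 is 0.811.
- DFS, RT: p0=0.688, n=40 gives r=34 and size 0.016. Power at 0.88 is 0.802.

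Both agree with the stated figure of over 80%. The plan gives no power for safety to reproduce.

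**Step 2: apply the same rule to safety, n=40.** At one-sided 0.025:

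- CRT, p0=0.50: P(X ≥ 27)=0.019 and P(X ≥ 26)=0.040, so r=27 (67.5%).
- RT, p0=0.39: r=23 (57.5%), size 0.014.

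| Excess over benchmark | CRT vs 50%, one-sided 0.025 | CRT vs 50%, one-sided 0.05 (r=26) | RT vs 39%, one-sided 0.025 |
|---|---|---|---|
| +10 points | 21% | 32% | 18% |
| +15 points | 44% | 57% | 39% |
| +20 points | 70% | 81% | 64% |
| +25 points | 90% | 95% | 85% |

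Against 50%, 80% power is reached at a true rate of about 72% (one-sided 0.025) or 70% (one-sided 0.05). The two-sided exact 0.05 test has the same upper cut-off of 27.

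Fisher's test, as named in 8.1.1, needs the size of the historical group, which the documents do not give. For an assumed 100 to 250 patients at one-sided 0.025 it rejects at 28/40 or more. Power is 13%, 31%, 58% and 82% at true rates of 60%, 65%, 70% and 75%.

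**Step 3: what a non-significant result allows.** At one-sided 0.025, 26/40 (65%) is not significant, and its exact 95% CI is 48% to 79%. Even 20/40, equal to the benchmark, has a CI of 34% to 66%. Excluding a true rate of 65% or more, with 80% power when the truth is 50%, would take about 94 patients.

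**Step 4: effect of the benchmark if weekly dosing is milder.** The true rate is background plus 20 points, tested against 50% with r=27.

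| Assumed weekly background | True rate at +20 | Flagged against 50% | Flagged against the assumed background |
|---|---|---|---|
| 30% | 50% | 2% | 68% |
| 35% | 55% | 8% | 68% |
| 40% | 60% | 21% | 69% |
| 45% | 65% | 44% | 70% |

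With no schedule effect (background 50%), the figure is the 70% in Step 2.

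**The case against.** **The plan draws no such inference.** A reader might infer that the sponsor will take a non-significant test as proof of safety, or that the primary safety hypothesis rests on this test. The documents support neither. Section 8.1.1 states an expectation, objective 1 is worded as estimation, and 8.2.4.1 begins with descriptive statistics. The hypothesis in 3.1 also concerns interruption of standard therapy, which the lead-in dose-limiting-toxicity rule (5.2.2.3) addresses without using the 50%. The data safety monitoring board reviews adverse event frequency and severity as well (10.6.2). This stands. What remains is that the formal comparison has no rule for reading a null result and no planned interval, whereas DFS and overall survival have 95% CIs.

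**The direction of bias is not established.** A reader might also infer that the comparison is biased towards finding no added toxicity. The documents do not show this. The only weekly-versus-standard statement comes from nasopharyngeal cancer, which this trial excludes, and the bolus statement compares with radiation alone. Section 4.2.2.2 also relies on cumulative dose and cooperative-group practice. Adverse events are recorded here from consent, through the pre-surgical dose and surgery, to 30 days after treatment ends (7.2), and feeding-tube placement is recorded as an adverse event (5.2.2.2.8). Either could raise the observed rate. The historical collection window is not given. This stands too: the schedule is one reason the benchmark may be too lenient, not a demonstrated net bias.

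**Power is not low everywhere.** At 25 points it is about 90% in CRT and 85% in RT. The limitation concerns moderate excesses, up to about 20 points.

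**Conclusion.** The concern holds in this form. The CRT benchmark is an unlabelled bolus-cisplatin rate, by the protocol's own account, applied to a weekly-cisplatin arm. It may be too lenient and partly mask toxicity added by pembrolizumab, but size and net direction are uncertain without a weekly rate. The 30% to 45% range, over which a 20-point excess is flagged 2% to 44% of the time, is illustrative.

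The power limitation does not depend on that premise and applies to both arms. A 15-point excess is detected 44% of the time in CRT and 39% in RT at one-sided 0.025, a level borrowed from the DFS test; in CRT it is 57% at one-sided 0.05. A non-significant result would not show that no undue toxicity was added. The cisplatin-schedule mismatch affects only the CRT arm.

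**What to change.** In 8.1.1 and 8.2.4.1:

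- Make the main safety result for each arm the proportion of patients with grade 3-4 events, which is the benchmark's definition, with an exact 95% CI. Report grade 5 events separately.
- Show 50% and 39% as historical context, labelling the 50% as a bolus-cisplatin rate.
- Treat the exact tests in both arms as descriptive.
- State that a non-significant result will not be read as absence of added toxicity.

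The cost is SAP wording and a more cautious safety statement. No extra patients or data are needed, and the lead-in rule and monitoring-board review are unaffected.
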